#### **8.1.5 Adverse Event Collection Period**

[figure not shown]
All AEs reported from the time of study drug administration until 70 days following discontinuation of study drug administration will be collected, whether solicited or spontaneously reported by the subject. In addition, protocol-related serious and non-serious AEs will be collected from the time the subject signed the study-specific informed consent.

Serious and non-serious AEs occurring after the study-specific informed consent is signed but prior to the initial dose of study drug will be collected **only** if they are considered by the Investigator to be causally related to the study-required procedures.

AE information will be collected as shown in [Figure 8-1](#).

**Figure 8-1 Adverse Event Collection**

AE = adverse event; SAE = serious adverse event.

\* Only if considered by the Investigator to be causally related to study-required procedures.

### 8.1.7 Pregnancy Reporting

Pregnancy in a study subject must be reported to the Sponsor within 24 hours of the site becoming aware of the pregnancy. Subjects who become pregnant during the study must be discontinued.

All subjects should be informed that contraceptive measures (refer to [Section 4.3](#) Contraception Recommendations) should be taken throughout the study and for at least 6 months after the last dose of study drug. Male subjects should be informed that contraceptive measures should be taken by their female partner.

Information regarding a pregnancy occurrence in a study subject and the outcome of the pregnancy will be collected. In the event of a pregnancy occurring in the partner of an enrolled subject, written informed consent for release of medical information from the partner must be obtained prior to the collection of any pregnancy-specific information, and the pregnancy will be followed to outcome. In the event a study subject or the partner of an enrolled subject delivers a baby, they will be asked to provide information including the following will be requested: date of delivery, birth weight and length, boy or girl, problems during pregnancy or delivery, and if the baby has any birth defects.

Pregnancy in a study subject is not considered an AE. However, the medical outcome of an elective or spontaneous abortion, stillbirth or congenital anomaly is considered an SAE and must be reported to AbbVie within 24 hours of the site becoming aware of the event.

## **8.2 Product Complaint**

### **8.2.1 Definition**

A Product Complaint is any Complaint (refer to [Section 8](#) for the definition) related to the biologic or drug component of the product or to the medical device component(s).

For a product this may include, but is not limited to, damaged/broken product or packaging, product appearance whose color/markings do not match the labeling, labeling discrepancies/inadequacies in the labeling/instructions (example: printing illegible), missing components/product, device not working properly, or packaging issues.

Any information available to help in the determination of causality to the events outlined directly above should be captured.

### **8.2.2 Reporting**

Product Complaints concerning the investigational product must be reported to the Sponsor within 24 hours of the study site's knowledge of the event via the Product Complaint form. Product Complaints occurring during the study will be followed-up to a satisfactory conclusion. All follow-up information is to be reported to the Sponsor (or an authorized representative) and documented in source as required by the Sponsor. Product Complaints associated with AEs will be reported in the study summary. All other complaints will be monitored on an ongoing basis.

Product Complaints may require return of the product with the alleged complaint condition. In instances where a return is requested, every effort should be made by the Investigator to return the product within 30 days. If returns cannot be accommodated within 30 days, the site will need to provide justification and an estimated date of return.

The description of the complaint is important for AbbVie in order to enable AbbVie to investigate and determine if any corrective actions are required.

### **8.2.3 Events Commonly Associated in Study Population with Advanced Solid Tumors and/or Progression of Underlying Malignancy**

Certain AEs are anticipated to occur in the study population at some frequency independent of drug exposure. Such events include known consequences of the underlying disease or condition under investigation (e.g., symptoms, PD).

A list of AEs associated with advanced solid tumors is provided in [Appendix 13.10](#). These AEs are preferred terms coded according to the latest version of the Medical Dictionary for Regulatory Activities (MedDRA) dictionary; the AEs may occur alone or in various combinations and are considered expected for reporting purposes for this protocol. Although exempted from expedited reporting to Health Authorities and IRBs as individual cases, if these AEs meet serious criteria these SAEs must be reported to AbbVie within 24 hours of the site

being made aware of the SAE (as required in [Section 8.1.6](#)). For deaths related to disease progression (coded to malignant neoplasm progression), the date and cause of death will be recorded on the appropriate case report form (CRF), but the event will not be expedited as an Individual Case Safety Report (ICSR) to regulatory authorities ([Section 8.1.4](#)).

### **8.3 Appropriateness of Measurements**

The safety measures that will be used in this trial are considered standard procedures for evaluating the potential adverse effects of study medications. AEs and, when applicable, clinical laboratory data will be graded using NCI CTCAE, version 4.03.

Response will be assessed according to RECIST v1.1 ([Eisenhauer 2009](#)), which includes standard criteria for evaluating response in solid tumors. Prostate cancer is assessed by PCWG3 criteria. The intervals of evaluation in this protocol are appropriate for disease management.

Standard tests will be performed to detect the possible presence of specific antibodies to study drug. PK assessments for drug activity are also common in clinical studies.

## **9. Data Quality Control and Quality Assurance**

### **9.1 Site Training and Monitoring Procedures**

A study manual that includes instructions for study compliance and CRF completion will be provided. Prior to the enrollment of subjects at the site, the Sponsor or its designated clinical and medical personnel will review the following items with the Investigator and clinic staff:

- The protocol, study objectives, eligibility requirements, study procedures, registration and withdrawal processes
- Current Investigator's brochure
- Recording and reporting AEs and SAEs
- Enrollment goals and study timelines
- The CRF completion process and source documentation requirements
- Monitoring requirements
- Institutional Review Board/Independent Ethics Committee (IRB/IEC) review and approval process
- Informed consent process
- Good Clinical Practice guidelines and related regulatory documentation requirements
- Key study team roles and responsibilities
- Investigational product storage, accountability, labelling, dispensing and recordkeeping
- Subject coding
- Study samples/specimen collection, handling and shipping
- Protocol compliance
- Clinical study recordkeeping, document retention, and administrative requirements

Monitoring visits will occur periodically, with frequency dependent on the rate of enrollment and workload at each site. During monitoring visits, the Sponsor representative will review regulatory documentation, CRFs, source documentation, investigational product storage, preparation, and accountability. The CRFs will be reviewed for completeness, adherence to the provided guidelines, and accuracy compared to the source documents. The Investigators must ensure that the monitor is allowed to inspect all source documents pertinent to study subjects, and must cooperate with the monitor to ensure that any problems noted in the course of the trial are resolved. The Investigator must maintain a comprehensive and centralized filing system of all study-related documentation that is suitable for inspection by the Sponsor or its designated monitors and by quality assurance auditors, or representatives of regulatory authorities.

### **9.2 Data Management Procedures**

The Sponsor or its designee will provide CRF Completion Guidelines for eCRF data entry. Study specific data management procedures will be maintained in the data management plan. Queries

resulting from edit checks and/or data verification procedures will be posted electronically in the eCRF.

### **9.3 Access to Source Data**

The Investigator will permit the Sponsor's representatives to monitor the study as frequently as the Sponsor deems necessary during or after the completion of the study to determine that protocol adherence and data recording are satisfactory. Appropriate measures to protect subject confidentiality are to be employed during monitoring. The CRFs and related source documents will be reviewed in detail by the monitor at each site visit. Original source documents or certified copies must be provided to the Sponsor for review. This review includes inspection of data acquired as a requirement for participation in this study and other medical records as required to confirm that the information contained in the CRFs, such as disease assessments, AEs, and concomitant therapies, is complete and correct. Other study records, such as correspondence with the Sponsor and the IRB/IEC and screening and drug accountability logs will also be inspected. All source data and study records must also be made available during or after completion of the study for inspection by representatives of regulatory authorities. In the event of an inspection by regulatory authorities, the Sponsor may be available to assist in any preparations. All pertinent study data must be made available as requested to the regulatory authority for verification, audit, or inspection purposes.

### **9.4 Accuracy and Reliability of Data**

The Sponsor or its designee shall take steps to assure the accuracy and reliability of data, including:

- The selection of qualified Investigators and appropriate study centers.
- Review of protocol procedures with the Investigators and associated personnel prior to the study.
- Periodic monitoring visits by the designated monitor(s).
- Review of CRFs for accuracy and completeness by the designated monitor(s) during monitoring visits to the study centers. Any discrepancies will be resolved with the Investigator or designees as appropriate.

### **9.5 Quality Assurance Procedures**

The Quality Assurance group or its designee may conduct audits at the clinical site or other study-related facilities and organizations during or at any time after the study. Audit reports will be retained by the Sponsor's Quality Assurance group or its designee as part of the written record.

## **9.6 Data Handling and Recordkeeping**

### **9.6.1 Data Handling**

It is the Investigator's responsibility to ensure the accuracy, completeness, legibility, and timeliness of the data reported to the Sponsor in the CRFs and in all required reports. The CRFs should be captured in the Sponsor EDC system within ten (10) business days of the subject's visit to the site. Data reported on the CRF that is derived from source documents should be consistent with the source documents or the discrepancies must be explained.

Any change or correction to a CRF must be maintained in an audit trail within the electronic data capture system. Data changes may only be made by those individuals so authorized. The Investigator must retain records of the changes and corrections, written and/or electronic. Prior to database lock the Investigator must review and approve the completed electronic CRFs to verify their accuracy.

### **9.6.2 Investigator Record Retention**

The Investigator shall retain study drug disposition records and all source documentation (such as original ECG tracings, laboratory reports, and in-patient or office patient records) for the maximum period required by the country and institution in which the study will be conducted, or for the following periods, whichever is longer: for at least 2 years after the last approval of a marketing application in an International Conference on Harmonisation (ICH) region and until there are no pending or contemplated marketing applications in an ICH region or for at least 2 years after the relevant authority has been informed of the discontinuation of clinical development of the study drug. The Investigator may not destroy any records associated with the study without obtaining the prior, written consent of the Sponsor. If the Investigator withdraws from the study (due to relocation, retirement, etc.), the records will be transferred to a mutually agreed upon designee, such as another Investigator or IRB/IEC. No records shall be transferred without prior, written authorization from the Sponsor or its designee.

## 10. Data Analysis and Statistical Methods

This section provides the key details of the statistical analyses to be performed using data captured according to this protocol. Further details on planned analyses for the data captured in this protocol will be provided in the Statistical Analysis Plan (SAP).

### 10.1 Determination of Sample Size

Up to approximately 318 subjects are expected to participate in this two-part trial.

In Part A, up to approximately 144 subjects may be enrolled, assuming 3 dose-escalation cohorts of 6 subjects each (18 subjects) across 8 disease cohorts. The exact number will depend on the number of cohorts required to reach the MTD in each disease, and the number of subjects enrolled in each disease-specific cohort.

In Part B, up to approximately 174 subjects may be enrolled, including approximately 19 subjects in each of the 5 disease-specific cohorts. The rationale for the sample size is based on the assumption that an ORR of around 15% would be indicative of efficacy worthy of further investigation given the advanced cancers and extensive treatment history in this study population. Additionally, an ORR below 5% would provide evidence of an ineffective treatment. The goal of the efficacy analyses is to provide a preliminary signal that the response rate may potentially be within that target range.

When Part B is enrolled, each disease-specific cohort will have approximately 25 subjects treated at the RP2D, including the Part A and Part B subjects. [Table 10-1](#) presents the 90% two-tailed lower exact confidence limits for selected response rates.

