### **Part B Expansion Cohorts**

To explore the recommended dosing regimen for distinct disease subsets, subjects will be enrolled in disease-specific expansion cohorts in Part B. The dose regimen(s) to be examined in the disease-specific cohorts will be at the MTD determined in Part A or a lower dose(s) and/or regimen(s), depending on the cumulative data. For example, a lower dose regimen may consist of a finite number of doses and/or a mixed-dose regimen, with all doses at or below MTD, but varying based on the cycle. The dose(s), regimen(s), and schedule(s) for the expansion cohorts will be determined by the Sponsor in consultation with the SMC.

In Part B, up to approximately 174 subjects may be enrolled, including approximately 19 subjects in each of the 5 disease-specific cohorts and up to 30 subjects each for Cohort 7 and Cohort 8. The goal of the Part B expansion is to provide further safety data and preliminary efficacy data for the selected dose regimens.

Response will be assessed by radiographic imaging at protocol-specified time points determined by the subject's dosing schedule. In the 6-week cycle schedule, tumor response will be assessed every 6 weeks during active study treatment until 24 weeks, then every 12 weeks, thereafter. Prostate cancer-specific assessments are described in [Appendix 13.6](#).

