### **PLANNED SAMPLE SIZE:**

Up to approximately 318 subjects are expected to participate in this two-part trial. Study accrual in Part A is approximately 144 subjects (depending on the number of cohorts required to reach the MTD). For Part B, approximately 174 subjects may be enrolled. The “Other NEC/NET” and “Other Solid Tumor” cohorts will each enroll 30 subjects. The rationale for the sample size is based on the assumption that an objective response rate (ORR) of around 15% would be indicative of efficacy worthy of further investigation, given the advanced cancers and extensive treatment history in this study population. Conversely, response rates less than 5% would indicate lack of efficacy. A sample size of 25 subjects would produce a 90% two-tailed confidence interval (CI) of 5.7% to 33.0% around an observed response rate of 16.0%.

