### 3. Investigational Plan

#### 3.1 Summary of Study Design

This is a multicenter, open-label study of rovalpituzumab tesirine in subjects with DLL3-expressing advanced solid tumors. The study will include 7 cohorts of subjects with the following cancers:

1. Malignant melanoma
2. Medullary thyroid cancer (MTC)
3. Glioblastoma
4. Large cell neuroendocrine carcinoma (LCNEC) of any origin
5. Neuroendocrine prostate cancer (NEPC)
6. High-grade gastroenteropancreatic neuroendocrine carcinoma (GEP NEC)
7. Other neuroendocrine carcinoma (NEC) and high grade neuroendocrine tumors (NET)
8. Solid tumors other than the above

As of protocol version 4.0, cohort 3 (Glioblastoma) is closed to enrollment. Specific guidance for cohort 3 (Glioblastoma) subjects (protocol version 3.0) are provided in Appendix 13.3.

Each disease-specific cohort will include two parts:

- Part A – Dose-Regimen Finding: Will involve disease-specific dose escalation, and possible dose-interval modification, to define the maximum tolerated dose (MTD) and/or possible recommended Phase 2 dose(s) (RP2Ds).
- Part B – Expansion Cohorts: Disease-specific expansion cohorts may be enrolled. Subjects in the expansion cohorts will be treated with a dose regimen(s) at or below the MTD and/or RP2D determined in Part A.

Dose limiting toxicities (DLTs) will be assessed during the DLT Evaluation Period (Section 3.1.3) for subjects in Part A, the dose regimen finding portion of the trial.

Safety will be monitored throughout the trial by the Safety Monitoring Committee (SMC) consisting at least of a Medical Monitor, Investigators, and the study biostatistician. The SMC will meet routinely to review the emerging safety, select pharmacodynamic and efficacy data, and may make dose-escalation and dosing-interval recommendations. The SMC may recommend further evaluation of safety at a given dose level, investigation of alternative dose regimens, including a dose level that is intermediate to the planned dose levels, modification of the dosing interval, limitation to the maximum number of doses, and/or elimination or cancellation of a dose level(s) in a cohort based on the experience in other cohorts. The SMC will also review cumulative safety data in order to identify safety concerns that may emerge due to cumulative exposure beyond the DLT window. The process for dose-escalation decisions and dose-interval recommendations, and the roles and responsibilities of the SMC may be detailed separately.

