### 3.1.2 Part B Expansion Cohorts

To explore the recommended dosing regimen for distinct disease subsets, subjects will be enrolled in disease-specific expansion cohorts in Part B. The dose regimen(s) to be examined in the disease-specific cohorts will be the MTD determined in Part A or a lower dose(s) and/or regimen(s), depending on the cumulative data. For example, a lower dose regimen may consist of a finite number of doses and/or a mixed-dose regimen, with all doses at or below MTD, but varying based on the cycle. The dose(s), regimen(s) and schedule(s) for each expansion cohort will be determined by the Sponsor in consultation with the SMC. For Part B, approximately 174 subjects may be enrolled. The “Other NEC/NET” and “Other Solid Tumor” cohorts will each enroll 30 subjects. Additional information regarding sample size is provided in [Section 10.1](#), Determination of Sample Size.

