**Table 10-1 Lower Exact 90% Two-Tailed Confidence Limits for Selected Objective Response Rate Results for 25 Subjects**

Number of Responses	Response Rate	Lower Confidence Limit
1	4.0%	0.2%
2	8.0%	1.4%
3	12.0%	3.4%
4	16.0%	5.7%

The final decision to pursue the clinical development of any disease-specific cohort will be based on safety evaluations, the complete results of the study, and other factors; fewer than 3 responses could be considered a discouraging result. When 3 or more responses are observed, there is approximately a 75% probability this occurs when the true rate is 15%, but less than 13% when the true rate is 5%. When 4 responses are observed, a 5% rate is excluded by the 90% confidence interval (CI) lower bound.

An interim futility analysis is planned for each cohort, which may have an impact on the number of subjects ultimately enrolled in Part B. The futility analysis is described in [Section 10.3.6](#).

- The Other NEC/NET and Other Solid Tumor cohorts will enroll subjects until all other disease cohorts complete enrollment, and are expected to enroll approximately 30 subjects each by the time of study completion.
- Details will be provided in the SAP.

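### The Part B total of 174 exceeds the sum of its stated cohorts (155) by 19 subjects, and the study total of 318 carries the same gap

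*Combined protocol and SAP*

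**What the plan says.** The Part B total of 174 appears in four places: Synopsis (Part B Expansion Cohorts), Synopsis (Planned Sample Size), Section 3.1.2 and Section 10.1.

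- **Synopsis, Part B Expansion Cohorts.** The sentence that gives the total also lists its parts: "approximately 19 subjects in each of the 5 disease-specific cohorts and up to 30 subjects each for Cohort 7 and Cohort 8".
- **Section 10.1.** "In Part B, up to approximately 174 subjects may be enrolled, including approximately 19 subjects in each of the 5 disease-specific cohorts". The text after Table 10-1 adds that the two remaining cohorts "are expected to enroll approximately 30 subjects each by the time of study completion".
- **Section 3.1.2.** "For Part B, approximately 174 subjects may be enrolled", followed by "The “Other NEC/NET” and “Other Solid Tumor” cohorts will each enroll 30 subjects".
- **Study total** (Synopsis, Planned Sample Size, and Section 10.1). "Up to approximately 318 subjects are expected to participate in this two-part trial".
- **Part A** (Section 10.1). About 144, from three dose levels of six subjects in each of eight disease cohorts.
- **Cohort 3** (Section 3.1). "As of protocol version 4.0, cohort 3 (Glioblastoma) is closed to enrollment".

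**The concern.** A planned sample size should follow from the cohort sizes given for it. Here the Synopsis puts the total and its parts in one sentence, and the parts fall short of the total by a whole cohort. Part A is counted over eight disease cohorts, while Part B is described as five plus two. Nothing says how the closed GBM cohort is treated in either figure. A reader therefore cannot tell whether Part B is meant to be 155, 174 or something between, or whether GBM subjects are included. What is at stake is the clarity of the headline enrolment figures, not the inference within any cohort.

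**Working it through.** **Inputs**

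| Quantity | Value | Source |
|---|---|---|
| Disease-specific cohorts in Part B (1, 2, 4, 5, 6) | 5 | Synopsis, Part B; Section 10.1 |
| Subjects in each | about 19 | Synopsis, Part B; Section 10.1 |
| Cohorts 7 and 8 | up to / about 30 each | Synopsis; Section 3.1.2; Section 10.1 |
| Stated Part B total | 174 | four places listed above |
| Part A | 3 × 6 × 8 | Section 10.1 |
| Stated study total | 318 | Synopsis, Planned Sample Size; Section 10.1 |

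**Reproducing the plan's totals**

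- Part A: 3 × 6 × 8 = 144, as stated.
- Study: 144 + 174 = 318, as stated. The addition is right, given 174.
- Part B: 5 × 19 + 2 × 30 = 95 + 60 = 155. The stated 174 is not reproduced.

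**Size of the gap**

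- Part B: 174 − 155 = 19, and 19/174 = 10.9%.
- Study: 144 + 155 = 299, then 318 − 299 = 19, and 19/318 = 6.0%.

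**Where 174 could come from**

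- Six disease-specific cohorts: 6 × 19 + 2 × 30 = 114 + 60 = 174, exact.
- Five cohorts at the full 25 subjects: 5 × 25 + 60 = 185, no match.
- Seven cohorts of 19: 133, no match. Eight cohorts of 19: 152, no match.

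Only the six-cohort count gives 174. The version 4.0 summary of changes attributes the edit to the number of disease-specific cohorts in this sentence to the removal of Cohort 3, and the sentence it shows still has 174. That indicates a likely origin. The contradiction itself lies wholly in the current text.

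**Could the open cohorts reach 174?**

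- With Cohorts 7 and 8 at 30 each, the five others would need (174 − 60)/5 = 22.8 subjects each, and 22.8/19 = 1.20, so 20% above the stated size. Section 10.1 plans about 25 at the recommended Phase 2 dose including Part A, which implies 25 − 19 = 6 from Part A. Then 22.8 + 6 = 28.8, not 25.
- With the five cohorts at 19, Cohorts 7 and 8 would need (174 − 95)/2 = 39.5 each, against the stated 30.

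**Allowing for GBM subjects already in Part B**

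The documents do not give this number. Call it k and assume 0 ≤ k ≤ 19. Then, at the stated cohort sizes:

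- Part B = 155 + k, from 155 to 174.
- Study total = 144 + 155 + k = 299 + k, from 299 to 318.

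The stated totals are met only at k = 19, a complete GBM expansion cohort.

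**The case against.** The strongest defence is that 174 is a deliberate ceiling over the life of the study. Cohort 3 is closed to enrolment, not deleted: its endpoints and response criteria remain, and the summary of changes refers to GBM subjects still on study. Part A's 144 plainly still counts all eight cohorts, so keeping GBM in Part B's total would be consistent. This is possible, but no passage says that any GBM subject entered Part B or that 174 includes them. The k term above covers the case, and one added line would settle it.

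A second defence is that the figures are loose. The total is an approximate maximum, and Section 10.1 describes 30 for Cohorts 7 and 8 as an expectation, with enrolment running until the other cohorts finish. That softens the comparison in Section 10.1, but the Synopsis gives 30 as an upper limit. A gap of exactly one cohort is hard to put down to rounding. The planned interim analysis is for futility, so it can reduce enrolment but does not account for 19 more. The replacement rule in Section 3.1.1 concerns evaluability for dose-limiting toxicity in Part A only.

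Two points of scope stand. The Section 10.1 sentence alone gives only the five cohorts of 19; the complete breakdown in one sentence is in the Synopsis. And no power figure, decision rule or interval depends on 174 or 318.

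**Conclusion.** The concern holds. The stated Part B total is 19 subjects above the sum of its stated cohorts, and the study total is 19 too high for the same reason. This takes the stated sizes of 19 and 30 at face value and leaves Part A at 144. If k GBM subjects entered Part B before closure, the unexplained number falls to 19 − k, and it disappears only for a full cohort of 19.

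The consequence is limited to the headline totals. The planned 19 per disease-specific cohort, the approximately 25 at the recommended Phase 2 dose, Table 10-1 and the futility probabilities are unaffected. It is a real error in a core protocol figure and should be corrected, but it does not undermine the design.

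**What to change.** - Restate Part B as approximately 155, showing 5 × 19 + 2 × 30, in both Synopsis passages, Section 3.1.2 and Section 10.1.
- Restate the study total as approximately 299 (144 + 155) in the Synopsis (Planned Sample Size) and Section 10.1.
- If GBM subjects were enrolled in Part B before Cohort 3 closed, give their actual number on a separate line and include it in both totals. If that number is 19, then 174 and 318 stand, but the text must say so.
- Leave Part A at 144 and note that it counts all eight cohorts opened, including the closed GBM cohort.

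The cost is a wording change in four places. The sponsor needs to look up one number, the GBM enrolment in Part B. No cohort size, table or futility rule changes.
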